[contact]
[contact]

SCHEMA

The Impact of CCR5 Inhibitor Treatment Intensification on CD4+ T-cell Recovery and Gene Expression Profiles in HIV-Infected Patients with Viral Suppression (Main Study)

Maraviroc Pharmacokinetics and Immunomodulatory Effects within the Central Nervous System (CSF Sub-Study)

Design:

CCTG 590 is a single-arm, open-label study to evaluate the impact of therapy intensification of Maraviroc (MVC) (a CCR5 inhibitor) to a stable suppressive HIV antiretroviral regimen on the rate of CD4+ T-cell recovery and gene expression profiles. Subjects on a stable first-line HIV regimen with continued viral suppression and sub-optimal CD4+ T-cell counts will be eligible for this study. Those who are found to be eligible will have MVC (dose-adjusted to background HIV regimen) added to their current HIV regimen for 24 weeks. After the 24 week intensification, the MVC will be discontinued, the original antiretroviral regimen will be continued and the subjects will be followed for an additional 12 weeks.

CCTG 590s is a central nervous system (CNS) sub-study that will evaluate MVC cerebral spinal fluid (CSF) pharmacokinetics and immunomodulatory effects within the CNS. The primary eligibility criteria will be enrollment into the MVC parent study, ability to give informed consent to lumbar puncture (LPs). Pre-treatment LPs will be performed, followed by a LP at week 4 of MVC treatment intensification (i.e., “steady state”). For subjects willing to undergo more than one LP, an additional LP will be performed at week 24 of MVC treatment intensification.

Duration:

Total study duration is 36 weeks: 24 weeks of MVC treatment intensification, followed by an additional 12 weeks of continued monitoring on baseline antiviral therapy without MVC.

Sample Size: 30 subjects (17 subjects for the CSF Sub-Study)

Study Population:

HIV-infected patients receiving an initial stable antiretroviral regimen with 12 months or more of viral suppression (defined by HIV RNA below detection limits) will be offered enrollment into this study. Eligible patients must have

documented dates of initiation of first HIV regimen and have been on continuous treatment for at least 15 months. In addition, available laboratory data must include at least 3 measurements of CD4 count and plasma HIV RNA loads obtained within the 12 months prior to screening.

Regimen:

Maraviroc treatment intensification will be provided to all subjects dose-adjusted to each participant's background antiretroviral therapy:

A. with strong CYP3A4 inhibitors, including:

- Protease inhibitors (except tipranavir/ ritonavir)
- Delavirdine
- ketoconazole, itraconazole, clarithromycin, nefazadone, telithromycin
- Darunavir/r + etravirine

MVC 150 mg twice daily

B. with non-inducers/ non-inhibitors of CYP3A4, including:

- Tipranavir/ ritonavir
- Nevirapine
- All NRTIs
- Enfuvirtide

MVC 300 mg twice daily

C. with strong CYP3A4 inducers, including:

- Efavirenz, etravirine
- rifampin

MVC 600 mg twice daily

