3.0 STUDY DESIGN

3.1 Study Design (Main Study)

Thirty patients will be enrolled to evaluate the impact of adding the CCR5 inhibitor, MVC, to a stable suppressive HIV regimen on the rate of CD4+ T-cell recovery and gene expression profiles. At baseline whole genome expression (38,000 genes) profiles and extended flow cytometry will be performed on purified CD4+/CD8+ T-cells in all subjects. In addition, pre-MVC phase 2 CD4+ T-cell recovery rate will be estimated for each subject from historic laboratory data obtained during the 12 months prior to the baseline visit. All subjects will receive treatment intensification with MVC dose-adjusted to their background HIV regimen for 24 weeks. Regular visits will occur on weeks 2, 4, 8, 12 and 24 to assess efficacy, safety and medication tolerance. Additional microarray and

extended flow cytometric analyses will be performed at weeks 4 and 24 of MVC therapy. After 24 weeks of MVC treatment intensification, MVC will be discontinued, the original antiretroviral regimen will be maintained and subjects will return for a 12 week follow-up visit to evaluate on-going CD4+ T-cell recovery, continued HIV RNA suppression and any potential adverse events.

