4.0 SELECTION AND ENROLLMENT OF SUBJECTS

4.1 Inclusion Criteria (Main Study)

- 4.1.1 HIV-1 infection documented by a rapid HIV test or any licensed ELISA test kit and confirmed by a different method ELISA, Western blot, rapid HIV test, or plasma HIV-1 RNA assay at any time prior to study entry. Alternatively, if a licensed ELISA is not available, two HIV-1 RNA values >2000 copies/mL at least 24 hours apart by any CLIA certified laboratory may be used to document HIV-1 infection at any time prior to study entry.
- 4.1.2 All available CD4+ T cell counts within the last 12 months of screening below 350 cells/ mm^3 (minimum of 3 values obtained ≥ 30 days apart).
- 4.1.3 CD4+ cell count below than 350 cells/ mm^3 determined by site clinical laboratory within 30 days of screening.
- 4.1.4 Subject receiving a stable (for at least 6 months) antiretroviral regimen consisting of at least 2 NRTIs and either a protease inhibitor boosted with low dose ritonavir or an NNRTI. A stable regimen is defined as no additions or deletions for more than 14 cumulative days.
- 4.1.5 Subject considered to be receiving initial HIV regimen (history of medication substitution for toxicity is allowed).
- 4.1.6 All available plasma HIV RNA levels within the last 12 months are below the level of detection. Isolated values that are detectable but < 1000 copies will be allowed as long as the plasma HIV RNA levels before and after this detectable time point are undetectable – The subject should have a minimum of 3 values obtained ≥ 30 days apart.
- 4.1.7 Screening plasma HIV RNA levels below level of detection (< 50 copies RNA/mL using Roche Amplicor or < 75 copies/mL using Bayer bDNA) obtained by site clinical laboratory within 30 days of screening.
- 4.1.8 Greater than 90% adherence to HIV therapy within the preceding 30 days, as determined by self-report.

- 4.1.9 Laboratory values obtained by screening laboratories within 30 days of entry:
- Absolute neutrophil count (ANC) $\geq 750/\text{mm}^3$.
 - Hemoglobin ≥ 8.0 g/dL.
 - Platelet count $\geq 50,000/\text{mm}^3$.
 - Calculated creatinine clearance (CrCl) ≥ 50 mL/min as estimated by the Cockcroft-Gault equation:
 - * For men, $(140 - \text{age in years}) \times (\text{body weight in kg}) \div (\text{serum creatinine in mg/dL} \times 72) = \text{CrCl (mL/min)}$
 - * For women, multiply the result by 0.85 = CrCl (mL/min)
 - AST (SGOT), ALT (SGPT), and alkaline phosphatase $\leq 5 \times \text{ULN}$.

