6.2 Definitions for Schedule of Events – Timing of Evaluations

6.2.1 Evaluations Prior to Study Entry

Occur prior to the subject taking any study medications, treatments, or interventions.

Patient Registration

A patient identification number (PID) will be assigned to each patient screened for the study. PIDs will include a site code and three-digit extension. PIDs should not be reassigned even if the patient fails to enter the study. The PID must be included on every CRF and patient blood sample. Each site must maintain a master list of PIDs in a central location. The patient registration and inclusion/exclusion must be entered on-line at www.cfar.ucsd.edu/intranet

Screening Site Clinical Labs

If plasma HIV-1 RNA and CD4+ T-cell counts were obtained at a CLIA-approved lab no more than 30 days prior to screening and results are available then these labs do not need to be repeated. Otherwise, a plasma HIV-1 RNA level and a CD4 cell count measurement need to be done at screening. Please record actual dates laboratories were done in the CRF.

All other study screening laboratories must be determined within 30 days of study entry (Day 0). Screening and entry evaluations must be separated by at least 48 hours. Hematology, chemistry and pregnancy testing will be coordinated through the site's local laboratory and results will be tracked by the CCTG Data Center.

Once the screening laboratories have been done the patient will be evaluated for study eligibility if all other entry criteria are satisfied.

The total blood volume for screening labs is 20 mL.

If the HIV RNA or other laboratory values are outside the eligible range, the site may re-screen a patient on one occasion. However, the study will not pay for additional re-screening laboratories.

Pre-Entry

Specimens for extended flow cytometry and PBMC storage need to be shipped by each site in real-time to the central laboratory (UCSD).

The total blood volume for pre-entry labs is 20 mL.

Entry

The entry evaluation should be scheduled within 30 days of the screening visit. Plasma and serum for storage should be obtained, however, specimens will be stored then shipped in batch on week 36 (end of study) along with other plasma, PBMC and serum specimens. The first dose of study medication should be given and witnessed by the study coordinator **after** drawing the entry laboratories.

The total blood volume for entry labs is 73 mL.

Lumbar puncture – 25 mL cerebral spinal fluid

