6.3.2 Medical and Laboratory History

At screening a medical history will be obtained and must be recorded in the source documents. The medical history should include any previous HIV-related diagnoses and AIDS-defining events.

In addition, prior to obtaining screening laboratories, documentation of all historic plasma HIV-1 RNA load and CD4+ T-cell counts since initiation of first ARV regimen must be recorded in the source documents and on-line CRF form (www.cfar.ucsd.edu/intranet). **Of note:** a minimum of 3 CD4+ T-cell (below 350 cells/mm³) and HIV RNA values (below 50 copies/mL) obtained \geq 30 days apart must be obtained and recorded.

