9.4.3.1. Analysis of Secondary Objectives

Secondary analyses will include descriptive statistics and tests of significance between pre- and post-MVC intensification. All significance tests will be two-sided and no adjustment for multiple comparisons will be made. If necessary due to assumption failures, appropriate non-parametric statistical tests will be applied.

1. Differences in the change in CD4+ T-cell absolute count and percentage from baseline to week 4 and baseline to week 24 will be compared descriptively via separate paired Student t-tests. Repeated CD4+ T-cell absolute count measured at different time points (3 historic time-points, baseline, week 4, and week 24) will be treated as the outcome variable in a linear mixed-effects model. The primary fixed effects will include time, period (MVC vs. pre-MVC), and interaction between time and period; random effects will include both intercept and slope allowing each subject to have individual starting CD4+ T-cell counts and rate of change. Baseline covariate adjustment will be included if necessary. A significant interaction term between time and period with positive coefficient will indicate if the rate of CD4 recovery is greater during MVC compared to pre-MVC.

2. Differences in the rate of CD4+ T-cell recovery (absolute count and percentage) during MVC intensification in subjects receiving a PI/r- vs. NNRTI-based regimen will be compared via the linear mixed effects model. The fixed effects will include time, regimen (PI/r vs NNRTI), and regimen-by-time interaction; random effects will include both intercept and slope. The regimen-by-time interaction term in the model will indicate the difference in CD4+ T cell recovery rates between the two regimen groups. Baseline covariate adjustment will be included if necessary.

3. Differences in gene expression profiles between subjects receiving a PI/r vs. NNRTI-based regimen at baseline and weeks 4 and 24 will be examined by comparing the gene lists generated in the primary analysis by regimen type. If necessary, statistical modeling will include a dichotomous variable to indicate regimen type.

4. Differences in the proportion of CD4+/CD8+ T-cell immune activation, maturation, regulatory and apoptosis markers between baseline and weeks 4 and 24 will be compared cross-sectionally via McNemar's test or paired t-tests as appropriate.

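### The pre-MVC CD4 slope is the only control for objective 1.2.1, yet its three historic counts may span as little as 60 days and the model leaves other recorded counts unused

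*Combined protocol and SAP*

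**What the plan says.** Section 3.1 states that the pre-MVC "recovery rate will be estimated for each subject from historic laboratory data obtained during the 12 months prior to the baseline visit". The rules on which counts must exist are looser. The Schema says the data "must include at least 3 measurements of CD4 count and plasma HIV RNA loads obtained within the 12 months prior to screening" and gives no spacing. Criterion 4.1.2 asks for a "minimum of 3 values obtained ≥ 30 days apart", and 6.3.2 repeats that spacing. No section sets a minimum distance between the first and last count.

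Section 9.4.3.1, item 1, fits a linear mixed model to six counts per subject: "3 historic time-points, baseline, week 4, and week 24". On the model terms it says: "The primary fixed effects will include time, period (MVC vs. pre-MVC), and interaction between time and period". Intercept and slope are random. It does not say which three historic counts are used when more exist, nor whether the baseline count belongs to the pre-MVC or the MVC period.

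More data are collected than the model uses. Under 6.3.2, "documentation of all historic plasma HIV-1 RNA load and CD4+ T-cell counts since initiation of first ARV regimen must be recorded". Section 6.2.1 has the first dose given after the entry bloods are drawn, and says: "Screening and entry evaluations must be separated by at least 48 hours".

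**The concern.** There is no concurrent control arm. Objective 1.2.1 and hypothesis b in 2.3.1 compare the CD4 slope on MVC with the same subject's slope before it. The precision of a slope depends on how widely the counts are spread in time, and the plan controls their number and minimum spacing but not their spread. A subject with three monthly counts just before entry meets every rule and still says little about a recovery rate that section 2.1 puts at 2 to 10 cells/mm³ per month. If many subjects were like this, a null slope comparison would be hard to tell apart from an imprecise control.

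**Working it through.** The plan gives no SD, SE or power for the CD4 slope, so there is no figure to reproduce; the table in 9.3 concerns gene expression.

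**Inputs from the documents.** N = 30. Three historic counts at least 30 days apart. Entry 2 to 30 days after screening (6.2.1). On-MVC counts at weeks 4 and 24, which are 0.92 and 5.52 months. Expected slope 2 to 10 cells/month. Reference effect +32 cells over 24 weeks (section on impact on CD4 recovery), i.e. 32/5.52 = 5.8 cells/month.

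**Assumptions.** Within-subject CD4 SD 30 to 50 cells/mm³; random-intercept SD 60; random-slope SD 3 cells/month; two-sided alpha 0.05. Entry is counted as pre-MVC unless stated.

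**Minimum span.** 2 × 30 = 60 days for the historic counts. If they end at screening, adding entry gives 62 to 90 days.

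**Per-subject slope.** SE = SD/√Sxx, where Sxx is the sum of squared deviations of the count times, in months.

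| Pre-MVC counts (months) | Sxx | SE at SD 30 / 40 / 50 |
|---|---|---|
| −3, −2, −1, 0 | 5 | 13.4 / 17.9 / 22.4 |
| −7, −4, −1, 0 | 30 | 5.5 / 7.3 / 9.1 |
| −12, −8, −4, 0 | 80 | 3.4 / 4.5 / 5.6 |
| −12, −11, −10, 0 | 92.75 | 3.1 / 4.2 / 5.2 |

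The 12-month design carries 80/5 = 16 times the information of the late cluster. The last row is also a 60-day historic cluster, but an early one; with the entry count it is at least as informative as even spacing.

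**Study level, all subjects alike.** SE of mean slope change = √(SE_pre² + SE_on²)/√30. For weeks 4 and 24, Sxx = 10.58, so SE_on = 40/√10.58 = 12.3 at SD 40.
- 12-month spans: √(4.5² + 12.3²)/√30 = 2.39.
- All 30 at the late-cluster minimum: √(17.9² + 12.3²)/√30 = 3.96.
- All 30 with the −7, −4, −1, 0 pattern: √(7.3² + 12.3²)/√30 = 2.61.

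**Study level, mixtures.** The mixed model weights subjects by information, so the SE comes from generalised least squares on the model in 9.4.3.1, with the remaining subjects on 12-month spans. These values are the SE of the time-by-period interaction in cells/month.

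| Share at the late-cluster minimum | SD 30 | SD 40 | SD 50 |
|---|---|---|---|
| 0% | 1.79 | 2.39 | 2.99 |
| 50% | 1.93 | 2.54 | 3.14 |
| 100% | 2.97 | 3.96 | 4.95 |

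At SD 40, half the sample at the minimum raises the SE by 2.54/2.39 − 1 = 6%; all 30 raises it 3.96/2.39 = 1.66-fold. Power for 5.8 cells/month, Φ(5.8/SE − 1.96), is about 68%, 63% and 31% for the three rows.

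**If entry is placed in the MVC period (SD 40).** Three-monthly counts (−9, −6, −3) for everyone give 2.45. With half the subjects at a 60-day cluster instead, the SE is 2.51, 2.64 or 2.91 as the cluster ends about 2 days before entry, sits at −3, −2, −1, or sits at −7, −6, −5. With all 30 at the cluster ending 2 days before entry it is 5.5.

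**The case against.** The strongest reply is that the comparison is pooled over 30 subjects in one mixed model and is not read off individual slopes. Subjects with short spans are down-weighted, and at SD 40 the on-MVC slope (per-subject SE 12.3) already contributes more error than a well-spread pre-MVC slope (4.5). Half the sample at the minimum then costs only about 6%. This stands. It is somewhat sensitive to placement: with entry in the MVC period and clusters at −7, −6, −5 months, the half-and-half cost is 2.91/2.45 − 1 = 19%.

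It is also true that three is a floor, that the entry count lengthens the pre-MVC span, and that section 9.1 calls this a pilot powered for gene expression with CD4 slope as a secondary analysis. Those points stand too. They do not answer the gap in 9.4.3.1: further counts are on record, but the text admits only three, with no selection rule.

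A reader might infer that the study's control slope is almost uninformative, or that nearly two thirds of the sample is in effect lost (1 − (2.39/3.96)² = 64%). The documents do not support this. It requires all 30 subjects to sit at the late-cluster minimum, the distribution of spans is not given, and the SDs are assumed. Nor is every 60-day historic cluster poor, as the −12, −11, −10 pattern shows.

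**Conclusion.** The point holds as a limited loss of precision. The rules allow the historic counts to span 60 days, and a subject whose counts cluster just before entry has a slope SE of about 13 to 22 cells/month (entry included, 30 days after the last count), larger than the whole expected range of 2 to 10. Such a subject adds little to the only control available, and pooling does not rescue the per-subject rate that 3.1 promises. For the study, at SD 40, the SE of the slope change runs from about 2.4 (12-month spans) through about 2.5 (half at the minimum) to about 4.0 (all 30). The span rule in itself brings no bias, and no stated sample-size or power figure is wrong. The magnitudes rest on the assumed SDs and on an unknown spread of spans; the textual gap does not.

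**What to change.** Leave eligibility unchanged and amend 9.4.3.1, item 1:

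1. Replace the three historic time points with all recorded CD4 counts taken under suppression in the 12 months before baseline.
2. Where a subject's pre-MVC counts, entry included, span less than about 6 months, extend that subject's window back using the suppressed phase 2 counts recorded under 6.3.2, that is, those after the first 3 months of ART.
3. State that the entry count, drawn before the first dose, belongs to the pre-MVC period.
4. Report a sensitivity analysis restricted to the 12-month window.

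The cost is a few lines of text, with no extra visit, blood draw or excluded subject. There are two downsides. Some windows will reach beyond the 12 months in 3.1, to a time when recovery may have been faster; the sensitivity analysis is there for that. And a subject near the 15-month treatment minimum in the Schema has about 15 − 3 = 12 months of phase 2 history, so there may be few or no earlier counts to add.

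A minimum-span entry criterion on the historic counts is not the better route. It would narrow recruitment to a 30-person pilot for a secondary analysis, and a 6-month rule would turn away the informative early-cluster subject.

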1.0 STUDY OBJECTIVES

1.1 Primary Objectives

1.1.1 To characterize changes in gene expression profiles associated with early (week 4) and late (week 24) MVC therapy intensification.

1.1.2 To evaluate the association of gene expression profiles induced by MVC on the rate of CD4+ T-cell recovery during MVC therapy intensification.

1.2 Secondary Objectives

- 1.2.1 To compare the rates of phase 2 CD4+ T-cell recovery prior to and during 24 weeks of MVC therapy intensification.
- 1.2.2 To evaluate the impact of MVC therapy intensification on persistent immune activation and maturation phenotype (as measured by flow cytometry) during viral suppression.
- 1.2.3 To characterize differences in the gene expression profiles associated with MVC therapy intensification in individuals receiving a PI/r- vs. NNRTI-based regimen.
- 1.2.4 To evaluate the safety and tolerability of adding MVC to a stable antiretroviral regimen as assessed by the rate of > grade 2 adverse clinical or laboratory events.
- 1.2.5 To characterize cerebral spinal fluid concentrations of MVC compared to plasma concentrations.
- 1.2.6 To evaluate the impact of MVC therapy intensification on persistent immune activation (as measured by soluble and cellular markers) in the central nervous system.

2.0 INTRODUCTION

2.1 Background (Main study)

Suboptimal CD4+ T-cell recovery during potent antiretroviral therapy (ART) is a common clinical dilemma with an incidence as high as 40% [1-4]. Reconstitution of CD4+ T-cells during viral suppression follows a biphasic pattern [5]. In the first three months of ART, CD4+ T-cells typically increase by 50 to 120 cells/mm³ [6-8] - primarily as a result of redistribution of T-cells into peripheral circulation [9, 10]. The magnitude of this early recovery is likely a function of prior T-cell destruction as lower CD4+ T-cell nadirs have been associated with limited immune recovery during therapy [2, 11]. This initial burst is followed by a second, slower, phase of T-cell repopulation (average rate of 2 to 10 cell/mm³ increase per month [6-8, 12]) which may continue for as long as 6 years [13]. This second phase is often termed the 'regenerative phase' as de novo T-cells are produced from the thymus and by peripheral expansion. However, in some individuals, the phase 2 CD4+ T-cell recovery plateaus and these patients fail to recover 'normal range' T-cells despite optimal viral suppression [3, 13].

We propose to evaluate the potential beneficial immunomodulatory-effects of MVC on CD4+ T-cell recovery during optimal viral suppression. Individuals with well-controlled HIV-infection on ART will undergo therapy intensification with MVC for 6 months followed by a 3 month post-intensification visit. The goals of this study include:

1. To determine the impact of MVC treatment intensification on host genomic responses. Whole genome (~38,000 genes) analysis on purified CD4+/CD8+ lymphocytes will be used to evaluate changes in gene expression patterns, in particular genes associated with proliferation, trafficking and activation, before and during MVC treatment intensification.
2. To evaluate differences in the rate of phase 2 CD4+ T-cell recovery before and during 6 months of MVC treatment intensification.
3. To characterize changes in immune T-cell subsets (activation, maturation and apoptosis) before and during MVC treatment intensification.
4. To develop a gene classifier of MVC treatment-responsive genes and propose a model of the impact of CCR5-inhibition on immune reconstitution during suppressive ART.

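### The CD4 slope test assumes the pre-MVC rate would continue without MVC, so slowing between the two windows can mask a benefit; the model also omits three on-MVC counts per subject that are already collected

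*Combined protocol and SAP*

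**What the plan says.** The Schema states that "CCTG 590 is a single-arm, open-label study", with "Sample Size: 30 subjects". Objective 1.2.1 is: "To compare the rates of phase 2 CD4+ T-cell recovery prior to and during 24 weeks of MVC therapy intensification". Section 9.4.3.1 item 1 tests it with a linear mixed model on six counts per subject ("3 historic time-points, baseline, week 4, and week 24"). On the mean structure it says: "The primary fixed effects will include time, period (MVC vs. pre-MVC), and interaction between time and period". Intercept and slope are random. Covariate adjustment is left open, and no curvature or time-on-ART term is named. The decision rule is: "A significant interaction term between time and period with positive coefficient will indicate if the rate of CD4 recovery is greater during MVC".

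Section 2.1 gives the natural history. Phase 2 recovery averages 2 to 10 cells/mm³ per month and may last up to 6 years, but "in some individuals, the phase 2 CD4+ T-cell recovery plateaus and these patients fail to recover" normal-range counts. No fraction or timing is given for the plateau.

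The data collected go well beyond the six counts. Section 3.4 and the laboratory schedule in 6.1 call for CD4 at weeks 2, 4, 8, 12 and 24. Section 6.3.2 requires that "documentation of all historic plasma HIV-1 RNA load and CD4+ T-cell counts since initiation of first ARV regimen must be recorded".

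**The concern.** With no control arm, each subject's own history is the only comparator, and the MVC period always comes later. The model therefore takes the pre-MVC slope, carried forward unchanged, as what would have happened without MVC. If recovery slows between the two windows for reasons unrelated to MVC, the on-MVC slope is lower and the interaction falls below zero. Covariates measured once at baseline and entered as main effects cannot represent a change of slope within a subject.

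The eligibility rules make such slowing possible. The Schema requires at least 15 months on ART, and section 3.1 takes the pre-MVC slope from the 12 months before baseline. A subject at the minimum is compared across months 3 to 15 and months 15 to 20.5.

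What is at stake is the direct test of objective 1.2.1 and of hypothesis b in section 2.3.1: a true gain could be offset by slowing and go undetected. Leaving out half or more of the on-treatment counts makes this worse, because the on-MVC slope then rests on two points per subject.

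**Working it through.** The plan gives no power, SD or alpha for the CD4 test, so there is no figure to reproduce.

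**Inputs from the protocol:** N = 30; phase 2 rate 2 to 10 cells/month; reference effect +32 cells at 24 weeks (section 2.2.1.2, CCR5-inhibitor meta-analysis). **Assumptions:** historic counts at months -12, -8, -4; baseline (month 0) coded pre-MVC, which the plan does not specify; within-subject SD 35; two-sided alpha 0.05; the same slope change in every subject.

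**Time scale.** 24 weeks = 24 × 7 / 30.44 = 5.52 months. The reference effect is 32 / 5.52 = 5.8 cells/month.

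**Interaction with no MVC effect (cells/month)**

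- Linear recovery throughout: 0.
- Already flat before the historic window: 0.
- A fraction f stops recovering exactly at entry, from slope s: -f × s. With s = 5, f = 25% gives -1.25 and f = 50% gives -2.5.
- Rate halving every 12 months, pre-MVC slope 6. The curve is -2^(-t/12), with values -2, -1.587, -1.260, -1 at months -12, -8, -4, 0. Its least-squares slope is 6.655 / 80 = 0.0832. Between weeks 4 and 24 the slope is (0.948 - 0.727) / 4.60 = 0.0481. The ratio is 0.578, and 6 × (0.578 - 1) = -2.5.
- Simulated plateaus at individual times (30 subjects, 15 to 48 months on ART, slope 6 before the plateau): about -0.64 if half plateau before entry, and about -1.8 if all plateau between month 3 and 5 months after entry.

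The working range is thus about -0.7 to -2.5 cells/month, or -0.7 × 5.52 = -4 to -2.5 × 5.52 = -14 cells over 24 weeks, against the cited +32. It is not a bound. With smooth slowing (2 to 10 cells/month at month 3, halving every 6 to 24 months, either baseline coding), the term runs from -0.4 to -4.7 at 15 months on ART, -0.06 to -1.3 at 36 months and 0 to -0.7 at 60 months.

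**Standard error.** In this balanced model the random intercept and slope cancel from the interaction, so SE = SD × √(1/S_pre + 1/S_post) / √30, where S is the sum of squared deviations of the measurement times in months. S_pre = 36 + 4 + 4 + 36 = 80.

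- Weeks 4 and 24 only: S_post = 200 weeks² × 0.0529 = 10.6. SE = 35 × √(0.0125 + 0.0945) / 5.48 = 2.09.
- Weeks 2, 4, 8, 12, 24: deviations from the mean of 10 weeks are -8, -6, -2, 2, 14. S_post = 304 × 0.0529 = 16.1. SE = 35 × √(0.0125 + 0.0622) / 5.48 = 1.75.

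**Power for a true +5.8 cells/month:** Φ((5.8 + bias)/SE - 1.96)

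| Bias | Six counts (SE 2.09) | All on-MVC counts (SE 1.75) |
|---|---|---|
| 0 | 79% | 91% |
| -0.7 | 68% | 83% |
| -2.5 | 35% | 47% |

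The extra counts recover precision but do not remove bias. With six counts and SD 30, 40 or 50, unbiased power is 90%, 68% or 49%.

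**The case against.** The best reply is that the protocol does not describe general slowing. In section 2.1, slower compares phase 2 with phase 1; phase 2 may run for 6 years; and the plateau affects some individuals. Entry requires every count in the prior 12 months to be below 350, so many subjects may already be flat when the window opens, and the term is then zero. This stands. It also rules out a stronger inference that a reader might draw, namely that the no-effect value of the interaction is always negative. Selection on counts below 350, simulated without any slowing, moved the term between about -0.7 and +1.0, so even the net sign is not fixed.

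A reader might also quote a much larger loss. A 6-month halving time with a pre-MVC slope of 6 gives about -4.1 cells/month, or 70% of +32. But that implies about 11 cells/month at month 3 for a subject 15 months on ART, and 32 for one at 24 months, above the protocol's average range of 2 to 10. The 12-month case (-2.5) implies 8 and 14, so it fits only near the minimum time on ART.

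A third tempting step is to make a log-time curve the main test. When subjects plateau at individual times, a simulation shows the bias moving only from -1.77 to -1.42. When recovery is truly linear, the log term adds a bias of about +0.5, because it mixes differences between subjects in time on ART with change within a subject.

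Finally, bias from slowing works against MVC and does not create a false claim of benefit; the plan nowhere says that a null result will be read as no effect; and section 9.1 makes this a secondary analysis in a pilot powered on gene expression. All of that is correct and limits the weight of the point.

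**Conclusion.** The point holds conditionally. The model rests on an untested assumption that the pre-MVC slope would have continued, and the protocol's own background gives a reason to doubt it for some subjects. If recovery slows between the historic window and the MVC period, the interaction is biased downward, by roughly 0.7 to 2.5 cells/month under the assumed patterns. If recovery is linear or already flat, there is no such bias. The halving times, plateau fractions, spacing of historic counts and SD are assumptions; the documents supply none of them.

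The omission of the week 2, 8 and 12 counts does not depend on any slowing. Under an SD of 35 it costs about 12 percentage points of power (79% against 91%) for an effect of the cited size.

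**What to change.** In section 9.4.3.1 item 1:

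1. Fit the stated model to all on-MVC CD4 counts (weeks 2, 4, 8, 12, 24) and to all counts in the 12-month historic window. The SE of 1.75 comes from the three added on-MVC counts.
2. Keep the linear fit as the main analysis.
3. Prespecify a sensitivity analysis that allows curvature, using all phase 2 counts recorded under 6.3.2. With T months on ART at entry and t months from entry, split log(T + t) into log T (time on ART at entry) and log((T + t)/T) (change within subject), and enter both. The split keeps differences between subjects from being read as change within a subject.
4. State that this sensitivity model only partly removes bias from plateaus that occur at individual times, and that a non-significant interaction is not evidence that MVC has no benefit.

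The cost is SAP wording and a little more analysis. No visit, sample or subject is added.
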